### 15.3 Intra-rater variability and time comparison

Comparing measurements for each ORG member between different runs resulted in median R of 0.85 (IQR 0.73 - 0.88), 0.81 (IQR 0.73 - 0.87) and 0.78 (IQR 0.66 - 0.84) for original raters 1, 2 and 3, respectively. Due to Ligence Heart automatic measurements being determined by the input, Ligence Heart had no variation in measurements between different runs and had R of 1.0 for all measurements (Table 4), resulting in significantly lower intra-rater variability ( $p < 0.05$ ).

ORG members on average took  $12:58 \pm 3:18$  minutes to analyze the same measurements in 58 TTE studies while Ligence Heart was significantly faster, taking on average  $2:59 \pm 1:02$  minutes to analyze the same studies ( $p < 0.05$ ).

**Table 4.** Comparison of correlation coefficients between different runs in original rater group and Ligence Heart.

Label	OR1 Run 1 vs Run 2	OR2 Run 1 vs Run 2	OR3 Run 1 vs Run 2	Ligence Heart Run 1 vs Run 2
RAMAD	0.86	0.86	0.82	1
AoA	0.57	0.73	0.65	1

UAB Ligence	Clinical Investigation Report	2021-04-09
		Rev: 1.0

AoS	0.86	0.83	0.83	1
STJ	0.51	0.77	0.59	1
AAo	0.73	0.46	0.72	1
LAD	0.83	0.83	0.8	1
LAV4A	0.85	0.92	0.84	1
IVSd	0.88	0.62	0.42	1
LVPWd	0.66	0.35	0.41	1
LVEDD	0.92	0.86	0.89	1
LVESD	0.83	0.88	0.78	1
LVEDV4A	0.88	0.81	0.84	1
LVESV4A	0.93	0.91	0.88	1
LVEDV2A	0.93	0.87	0.87	1
LVESV2A	0.96	0.92	0.88	1
RAA	0.9	0.89	0.88	1
RVB	0.75	0.74	0.78	1
RVM	0.73	0.75	0.71	1
RVOTPD	0.88	0.77	0.77	1
RVEDA	0.75	0.68	0.66	1
RVESA	0.7	0.68	0.61	1

*Pearson correlation coefficients between different runs for the same rater are shown. Since Ligence Heart performs all measurements automatically and the output is completely determined by input, it has a correlation coefficient of 1 for all measurements. Run 1 and run 2 refers to different repeats of the study by the same rater. OR1 – original rater one; OR2 – original rater two; OR3 – original rater three.*

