## 4.3 General description

In order to better understand the method of working of the software, it is convenient to separate the process of echocardiography exam into two steps:

1. Data acquisition. During the first step, the operator of an ultrasound machine manipulates a probe interacting with the patient in order to produce the echocardiographic images of the heart. The images are then saved and stored digitally in DICOM format.
2. Data analysis. Using medical image viewing software the acquired echocardiography images are opened, annotated, measured and clinical conclusions are drawn based on the generated data.

Having established these steps, it is important to identify how the process of echocardiography exam takes place in the specific case of using Ligence Heart. The first step (data acquisition) remains the same as a regular echocardiography exam in accordance with standard clinical setting and is in no way affected using Ligence Heart software. Ligence Heart software is used to perform the entirety of the second step. To fulfill its intended purpose, the software Ligence Heart is used as a post-processing tool that is accessible via the sonographer's/physician's workstation in the office or any other dedicated area for patient's clinical data analysis.

Ligence Heart is used as a post-processing tool to perform the second step (data analysis), during which the following processes take place:

UAB Ligence	Clinical Investigation Report	2021-04-09
		Rev: 1.0

1. Echocardiography images are loaded to the Ligence Heart software via integration to PACS or manual study DICOM files upload.
2. The analysis phase:
  - a) **Manual functionalities** - user of the software manually identifies the relevant structures or features, annotates them, measurement results are displayed in the viewer.
  - b) **Automatic functionalities** - the software has algorithms implemented, that allow automatic identification, annotation, and calculation of a number of relevant heart parameters. These algorithms are based on deep learning technology. The results provided by these algorithms must be reviewed and approved by a clinician.
3. A report is generated. The results of the whole study analysis process are summarized in a report. The report document provides a table of measurements performed, a summary template, an illustrations list of measurements made.  

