2.2. Manual analysis	
2.2.1. Login to the image viewer	Authentication/authorization to the software step needed to be able to access studies
2.2.2. Study selection	Selection of accessible study by filtering/searching step
2.2.3. View selection and adjustments	Study analysis step, physician sets the view mode of echocardiography image, performs annotations, or adjusts measurements already made by automated analysis
3. Calculation of measurements	Calculation of measurements based on the annotations on echocardiography image performed by the combination of manual and automatic functions
4. Report generation	Study analysis report, which consists of all annotations, measurements made along with automated suggested diagnosis text, is generated for review and approval of physician
5. Validation by medical professional	Medical professional validates all annotations and measurements made and adjusts the annotations if needed, updating the report respectively

UAB Ligence	Clinical Investigation Report	2021-04-09
		Rev: 1.0

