## **5.2 Objectives**

### **5.2.1 Primary Objectives**

UAB Ligence	Clinical Investigation Report	2021-04-09
		Rev: 1.0

4. Manual measurement analysis: To calculate the reliability of Ligence Heart manual functions that are used to perform echocardiographic measurements comparing it with the manual measurements performed with other CE marked state-of-the-art medical image viewers.
5. Automatic measurement analysis: To compare Ligence Heart automatic measurements accuracy, variance, and error rate with human physicians in real clinical setting.
6. Time used comparison: To compare Ligence Heart automatic measurement tool execution time with the time it takes a physician to perform the measurements manually.

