## 7.2 Subject Procedure

### Part 1

The purpose of the procedure in the Part 1 is to calculate the accuracy of Ligence Heart manual functions that are used to perform echocardiographic measurements comparing it with the accuracy of manual measurements performed with other CE marked state-of-the-art medical image viewers. Measurements made in Ligence Heart software will be compared with CE marked software “IntelliSpace Cardiovascular 5.1” (Phillips) and “EchoPAC” version 112 from GE Healthcare.

One cardiologist will perform 2D TTE measurements of each patient on each system 2 times. Time difference between repeated measures must be at least two days.

### Part 2

The purpose of the procedure in the Part 2 is to compare Ligence Heart automatic measurements accuracy and reliability with human cardiologists in real clinical setting.

Four physicians will make 2D TTE measurements of each subject study 2 times. Physicians cannot share thoughts or results between themselves. Time difference between repeated measures must be at least two days. Measurements of three physicians will be used in modeling and results of the 4th will be used as a validation with automated system.

During both parts, time used for the analysis of the 2D TTE images will be recorded. During manual 2D TTE image analysis, time it takes for physician to make measurements will be registered. Stopwatch starts when physician opens study in Ligence Heart and stops when all listed measurements are made. In the use case including automatic measurements, the time it takes for automatic system to make measurements and physician to correct/validate the results is registered.

Summary of the clinical investigation parts

#	Analysis	Purpose	TTE Examination Protocol	Measurements
Part 1	Manual Measurement Analysis	To calculate the accuracy of Ligence Heart manual functions that are used to perform echocardiographic measurements comparing it with the accuracy of manual measurements performed with other CE marked state-of-the-art medical image viewers.	One physician will make 2D TTE measurements of each patient on each system 2 times. Time difference between repeated measures must be at least two days.	
 
• AoS (PLA)
 
• RVB (A4CH)
 
• LVEDV (A4CH)
 
• LVEDV (A2CH)
 
• RVEDA (A4CH)
 
• RAA (A4CH)
 
• AV-Vmax
 

UAB Ligence	Clinical Investigation Report	2021-04-09
		Rev: 1.0

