## 12 Statistical Methods

### 12.1 Statistical Hypotheses

UAB Ligence	Clinical Investigation Report	2021-04-09
		Rev: 1.0

The following hypotheses will be tested with the statistical methods:

1. The manual functionalities of Ligence Heart provide equally accurate tools for echocardiography evaluation compared to other state of the art CE marked medical software.
2. Automatic functionalities of Ligence Heart software perform echocardiography image analysis with non-inferior accuracy compared to a cardiologist.
3. Automatic functionalities of Ligence Heart software perform echocardiography image analysis with lower intra-rater variability compared to a cardiologist.
4. Automatic functionalities produce measurement values faster than a cardiologist.

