at once. In contrast, machine learning in echocardiography publications often only describe the accuracy of a single isolated task, e.g. classification or segmentation and provide metrics that might not necessarily translate well into clinical practice. The literature review shows that even though several studies were validated in multi-centre clinical trials, nevertheless they were only validated on isolated tasks. For example, ML models were shown to be faster and more repeatable for quantification of LVEF (27–29). ML model for quantification of RVEF showed good agreement with cardiac magnetic resonance imaging (30). Automated left ventricle volume quantification did not significantly deviate from the manual method (31). The clinical practice, however, requires more measurements to be performed, rather than only LVEF, RVEF and left ventricular volumes, for a holistic evaluation of a patient.

The automatic functionalities additionally offer the advantage of reproducibility in re-analysis of the same echocardiographic studies. Even though deep neural networks used in Ligence Heart can be considerably complex, they will produce identical output given the same input. In our analysis, we have shown that there is considerable intra-observer variability which can be reduced by using an automated system. The benefits of automated systems for reduced intra- and inter- observer variability are shown by the research as well. A study by Asch evaluated a ML model for detection of reduced LVEF and showed higher consistency, sensitivity, and specificity for detection of reduced LVEF than human operators did, another study by Myhr found that automated LVEF measurements show smaller intra- and inter-operator variability than manual methods do (27,32).

Finally, the time taken by an automated system to perform the same measurements is generally shorter compared to a human operator. It may vary based on the hardware being used. The literature supports the claim that automated methods perform quicker than manual ones as it was shown by Myhr where acquisition and analysis for calculating LVEF for an automated system was  $94 \pm 23$  seconds whereas for a manual method it was  $115 \pm 15$  seconds (32). In our case we used an upper-mid level consumer grade NVIDIA 2080 RTX GPU, which is not beyond what is reasonably available to a healthcare organization.

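### Hypothesis 3 could not fail, because deterministic software is run twice on identical input, and the time endpoint has two conflicting definitions

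*Protocol*

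**What the plan says.** **Intra-rater variability.** Hypothesis 3 in section 12.1 reads: "Automatic functionalities of Ligence Heart software perform echocardiography image analysis with lower intra-rater variability compared to a cardiologist". Section 15.3 compares run 1 with run 2 by Pearson correlation. The three original raters have median R of 0.85, 0.81 and 0.78. The device has R of 1.0 on all 21 measurements, explained as follows: "Due to Ligence Heart automatic measurements being determined by the input, Ligence Heart had no variation in measurements between different runs". A p-value below 0.05 is attached. The Table 4 footnote and section 16.2 repeat that output is fixed by input.

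Section 4.3 says of the algorithms: "The results provided by these algorithms must be reviewed and approved by a clinician". The table of functional elements in section 4.11 adds: "Medical professional validates all annotations and measurements made and adjusts the annotations if needed".

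**Time.** The objective (item 3 in the synopsis, numbered 6 in section 5.2.1) is: "To compare Ligence Heart automatic measurement tool execution time with the time it takes a physician to perform the measurements manually". Hypothesis 4 is: "Automatic functionalities produce measurement values faster than a cardiologist". For the use case with automatic measurements, section 7.2 says: "the time it takes for automatic system to make measurements and physician to correct/validate the results is registered". The time row of the summary table in section 7.2 holds both versions, execution time under purpose and device plus physician time under examination protocol. Section 15.3 gives 12:58 ± 3:18 minutes for the original raters and 2:59 ± 1:02 for the device, p below 0.05, without saying what the 2:59 covers.

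**The concern.** A hypothesis test is informative only if the data could have gone the other way. Software whose output is fixed by its input shows zero variation when the same file is processed twice, whether its measurements are good or poor. The comparison therefore cannot separate a good device from a bad one. The value that reaches the report has passed through a clinician who may change it. No repeat reading of reviewed output is planned or reported, so the repeatability of the device as used is unknown.

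For time, execution alone and execution plus physician correction answer different questions. A reader cannot tell which one the reported result answers.

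Lower variability and faster analysis are two of the three performance claims for automation in section 4.2. Section 16.2 presents both as shown, and section 16.3 builds its benefit conclusion on them.

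**Working it through.** **1. Reproduce the reported correlations.** The medians and quartiles of the 21 values per rater in Table 4 are:

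- Rater 1: 0.85 (0.73 to 0.88)
- Rater 2: 0.81 (0.73 to 0.87)
- Rater 3: 0.78 (0.66 to 0.84)

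These match section 15.3, so the arithmetic there is right. The problem is what is compared.

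**2. Could hypothesis 3 have failed?** All 63 cardiologist coefficients are below 1 (maximum 0.96), and the device value is fixed at 1. The protocol does not name the test behind its p-value, so a sign test over the 21 measurements serves as illustration:

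p = 2 × 0.5^21 = 9.5 × 10⁻⁷

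This holds for any rater below 1 on all 21 measurements. A cardiologist with R = 0.999 throughout would lose by the same p-value.

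**3. Direction of the Pearson issue.** R ignores a constant shift between runs. The device has no shift, so the omission can only flatter the cardiologists. It does not create the device's advantage. It does mean that R is not a within-rater error in millimetres or millilitres. The Part 2 ANOVA in section 12.5.1 already supplies one, √MSE. Run is not a factor in that model, so shifts between runs remain in MSE.

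**4. Time, from the stated means.** 12:58 = 778 s and 2:59 = 179 s.

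- Difference: 778 − 179 = 599 s = 9:59
- Relative saving: 599 / 778 = 77%
- Share of the saving lost per minute of review, if review is not yet included: 60 / 599 = 10%

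**5. How much review would overturn hypothesis 4?** Assumptions: the ± values are SDs (198 s and 62 s), n = 58, review time is constant, and the within-study correlation ρ, which the protocol does not give, lies between −1 and 0.6.

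SD of difference = √(198² + 62² − 2ρ × 198 × 62); 95% limits = 599 ± t(57) × SD / √58

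| ρ | SD (s) | paired t | lower 95% limit (min) |
|---|---|---|---|
| −1 | 260.0 | 17.5 | 8.84 |
| 0 | 207.5 | 22.0 | 9.07 |
| 0.6 | 168.3 | 27.1 | 9.25 |

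The reported p below 0.05 reproduces throughout. Unrecorded review would have to add about 8.8 to 9.2 minutes per study before the lower limit reached zero, and 9:59 before the mean advantage vanished.

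**6. Values not returned.** From Table 3: RAMAD 4, LAV4A 2, LVEDV4A 2, LVESV4A 2, LVEDV2A 4, LVESV2A 4, RAA 4, RVB 3, RVM 3, RVEDA 3, RVESA 3. The total is 34 across 11 measurements.

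- Share: 34 / (21 × 58) = 34 / 1,218 = 2.8%
- Per study: 34 / 58 = 0.59
- If every measurement takes a cardiologist equal time (778 / 21 = 37 s), completing them by hand adds 0.59 × 37 ≈ 22 s per study, or 22 / 599 ≈ 4% of the gap

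**The case against.** **Hypothesis 3 is worded for the automatic functionalities, and the protocol is open about determinism.** Both are true. Testing unreviewed output is faithful to the hypothesis as written, and identical output on identical input is a real advantage over a human reader. The claim is true, but a p-value adds nothing to it, and it does not carry over to reviewed output.

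**A reader might infer that hypothesis 4 was tested on raw device output, so that the saving is inflated.** The documents do not establish this. Section 15.3 is silent, and section 7.2 says that correction and validation time is registered, so 2:59 may already contain it. Section 16.2 describes the automated system's time and says "It may vary based on the hardware being used", which leans towards execution alone. That evidence is weak, because run plus review would also vary with hardware.

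**A reader might infer that the speed claim fails, or that the missing values undermine it.** Neither follows. The protocol claims only that the device is faster, and step 5 shows how much review it would take to reverse that. The discarded studies are disclosed in section 15.2 and Table 3 and discussed in section 16.2, and their effect on time is small. What remains is that section 15.3 describes the two sides as doing the same measurements, which is not strictly so.

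**Conclusion.** The point holds in two parts.

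(a) The hypothesis 3 result was settled before any data were collected. Its p-value should not count as evidence, and the comparison is uninformative about repeatability after clinician review. This rests only on the protocol's own statements about determinism and does not depend on any accuracy result.

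(b) The time endpoint is internally contradictory between the objective and the procedure, and the content of 2:59 is unstated. If 2:59 includes review, the result stands and only wording changes. If it does not, the 77% saving on the stated means is too large by an amount that the documents do not allow one to compute. The conclusion that the device is faster would still hold short of roughly 9 added minutes per study, under the assumptions in step 5.

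**What to change.** **Hypothesis 3.** Remove the test and p-value from sections 12.1 and 15.3, and adjust the matching conclusion in section 16.2. State repeatability on identical input as a design property, and say that repeatability of clinician-reviewed output was not assessed. Report the cardiologists' within-rater error (√MSE from the Part 2 ANOVA) in measurement units, beside or in place of Pearson R. Note that R ignores shifts between runs, which if anything favours the cardiologists.

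**Time.** Align the objective (synopsis, section 5.2.1 and the purpose column of the section 7.2 table), hypothesis 4 and the section 15.3 result with the section 7.2 definition of device run plus physician correction and validation. State what 2:59 contains. Give the paired per-study difference with a 95% confidence interval. Show execution time as secondary, where it was recorded separately. State beside the result that 34 of 1,218 device values were not returned.

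**Cost.** Rewording, plus re-analysis of readings already taken and of times that section 7.2 already requires to be registered. The protocol does not show that run and review times were stored separately, so the split may not be recoverable. The stated time saving may become smaller.

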## 15.4 Summary of Safety

**Table 5.** Summary of Adverse Events.

Adverse events	Occurred events

Serious adverse events (AE):
 
Any untoward medical occurrence, unintended disease or injury, or untoward clinical signs (including abnormal laboratory findings) in subjects, users or other persons, whether or not related to the investigational medical device
 
NOTE 1: This definition includes events related to the investigational medical device or the comparator.
 
NOTE 2: This definition includes events related to the procedures involved.
	0

UAB Ligence	Clinical Investigation Report	2021-04-09
		Rev: 1.0

NOTE 3: For users or other persons, this definition is restricted to events related to investigational medical devices.	

Adverse device effects (ADE)
 
Adverse event related to the use of an investigational medical device
 
NOTE 1: This definition includes adverse events resulting from insufficient or inadequate instructions for use, deployment, implantation, installation, or operation, or any malfunction of the investigational medical device.
 
NOTE 2: This definition includes any event resulting from use error or from intentional misuse of the investigational medical device
	0

Serious Adverse Event (SAE):
 
Adverse event that
 
a) led to death,
 
b) led to serious deterioration in the health of the subject, that either resulted in
 
1) a life-threatening illness or injury, or
 
2) a permanent impairment of a body structure or a body function, or
 
3) in-patient or prolonged hospitalization, or
 
4) medical or surgical intervention to prevent life-threatening illness or injury or permanent impairment to a body structure or a body function,
 
c) led to fetal distress, fetal death or a congenital abnormality or birth defect.
 
NOTE 1: Planned hospitalization for a pre-existing condition, or a procedure required by the CIP, without serious deterioration in health, is not considered a serious adverse event.
	0

Serious Adverse Device Effect (SADE):
 
Adverse device effect that has resulted in any of the consequences characteristic of a Serious Adverse Event
	0

Unanticipated Serious Adverse Device Effect (USADE):
 
Serious adverse device effect which by its nature, incidence, severity or outcome has not been identified in the current version of the risk analysis report
 
NOTE: Anticipated serious adverse device effect (ASADE) is an effect which by its nature, incidence, severity or outcome has been identified in the risk analysis report.
	0

Unanticipated Adverse Device Effect (UADE):
 
Any serious adverse effect on health or safety or any life-threatening problem or death caused by, or associated with, a device, if that effect, problem, or death was not previously identified in nature, severity, or degree of incidence in the investigational plan or application, or any other unanticipated serious problem associated with a device that relates to the rights, safety, or welfare of subjects.
	0

Device deficiencies
 
Inadequacy of a medical device with respect to its identity, quality, durability, reliability, safety or performance
 
NOTE: Device deficiencies include malfunctions, use errors, and inadequate labelling
	0

UAB Ligence	Clinical Investigation Report	2021-04-09
		Rev: 1.0

Relevant corrective actions	None Needed
------------------------------------	-------------

## 16 Discussion and conclusions

### 16.1 Manual functionalities (Part 1)

Different types of manual measurements including area, distance and point measurements in B-mode and different spectral Doppler imaging modes have been tested and compared to two other CE marked medical image analysis platforms (EchoPAC by GE and Intellispace Cardiovascular by Philips). The measurement values obtained using the manual Ligence Heart functionalities did not show statistically significant variation when compared with other medical image analysis software. This proves that Ligence Heart can be used as medical image analysis software to analyze echocardiographic imaging data.

